#### 4.3.6 Study Termination Criteria

Any serious adverse event considered to be related to study treatment (see section 7.3.2.1 and 7.3.5) will be considered reason for termination of assigned intervention; participant will be followed up for cycle outcome and will contribute research data towards intent-to-treat analyses. This includes allergic reactions and liver toxicity. Women with elevation in liver function test with 3 times the upper limit of normal will be terminated from the study and will return to site for repeat testing every 48 hours until resolution.

All reports of liver toxicity will be reviewed by the DSMB (see section 7.3.4). If three (3) or more trial participants developed active liver disease, as defined below, this would be an unexpected significant risk requiring trial termination:

1. Alanine aminotransferase (ALT) or Aspartate aminotransferase (AST)  $\geq 8 \times$  upper limit of normal (ULN)
2. ALT or AST  $\geq 3 \times$  ULN and total bilirubin (TBL)  $> 2 \times$  ULN or International Normalized Ratio (INR)  $> 1.5$  or
3. ALT or AST  $> 3 \times$  ULN with appearance of fatigue, nausea, vomiting, right upper quadrant pain or tenderness, fever, rash, and/or eosinophilia ( $> 5\%$ ).

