## **2.6 Secondary Outcome Parameters**

The secondary outcome parameters will include:

- Changes in liver function between the 3 groups.
- Changes in estrogen levels (E2) between the 3 groups.
- Changes in endometrial thickness and ovarian characteristics between the 3 groups.
- Change in the pharmacokinetic parameters of EGCG and metabolites within each group.
- Difference in serum folate levels among wildtype MTHFR, MTHFR (C677T), and MTHFR (A1298C) patients.

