## **2.7 Statistical Analysis**

Since the number of patients for this study is minimal and multiple factors are of concern, descriptive statistics will be used, and the study is expected to be under powered to perform any formal statistical inference. The number, mean, standard deviation, median, interquartile range of the level of the pharmacokinetic parameters of EGCG and 2 of the major metabolites at different time points and the difference from screening to Visit 1, Visit 2 or Visit 4, and the changes in liver function, estrogen levels, endometrial thickness, and follicular measurements will be presented for the three treatment groups, and then stratified by age group and/or the presence or absence of uterine fibroid. For comparison, a two-way ANOVA will be used to compare the effects of the three treatments and the presence of fibroids on the above outcome parameters. With a sample size of 36 patients for the three treatment groups, which includes 18 subjects with uterine fibroids and 18 without uterine fibroids, with an alpha of 0.05, the power of the study would be 0.44 and 0.85 for a medium (0.25) or large (0.4) effect size, respectively. There are insufficient preliminary data

in the literature to support or not support the reasonableness of these effect sizes. For the comparison of serum folate levels among wildtype MTHFR, MTHFR (C677T), and MTHFR (A1298C) patients, ANOVA (unadjusted) and multivariate linear regression will be used.

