### 6.4 Difference in serum folate levels among wildtype MTHFR, MTHFR (C677T), and MTHFR (A1298C) patients. Statistical Analyses

Since the number of patients for this study is minimal and multiple factors are of concern, descriptive statistics will be used, and the study is expected to be under powered to perform any formal statistical inference. The number, mean, standard deviation, median, interquartile range of the level of the pharmacokinetic parameters of EGCG and 2 of the major metabolites at different time points and the difference from screening to Visit 1 or Visit 2 or Visit 4, and the changes in liver function, hormone levels, endometrial thickness and follicular measurements will be presented for the three treatment groups, and then stratified by age group and/or the presence or absence of uterine fibroid. Patients with a detectable EGCG level at the screening visit will be excluded. For comparison, a two-way ANOVA will be used to compare the effects of the three treatments and the presence of fibroids on the above outcome parameters. With a sample size of 36 patients for the three treatment groups, and 18 subjects with uterine fibroids and 18 without uterine fibroids, with an alpha of 0.05, the power of the study would be 0.44 and 0.85 for a medium (0.25) or large (0.4) effect size, respectively. There are insufficient preliminary data in the literature to support or not support the reasonableness of these effect sizes. For the comparison of serum folate levels among wildtype MTHFR, MTHFR (C677T), and MTHFR (A1298C) patients, ANOVA (unadjusted) and multivariate linear regression will be used.

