### *7.3.4 Adverse Event Reporting*

Adverse events deemed non-serious will be recorded throughout study participation from the start of study drug through one week after the last dose of study medication and reported to the DCC. Non-serious adverse events will be reported to the DSMB quarterly.

Supervising Institutional Review Boards (IRBs) will be notified by local investigators of adverse events occurring at their institution according to their reporting requirements. Investigators also will notify the medical monitor and DCC within 24 hours after knowledge of a death or of an event that is life-threatening, that results in hospitalization or prolongation of hospitalization, or that involves a persistent or significant disability or incapacity. Study staff will collect information regarding the treatment provided, outcome, and presumed relationship to study, and a narrative description of the event. The study staff will provide updated reports to the DCC as new information becomes available. DCC personnel will review the data and query the clinical sites for clarification and additional information. In addition, the DCC will provide the information to the Data and Safety Monitoring Board (DSMB) as part of their safety review.

The DCC will provide study-wide summary statistics (not filtered by treatment group) of adverse events to the single IRB annually and upon request to all sites on an annual basis for submission to their IRBs.

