### **7.8 Reporting**

Administrative Reports will be prepared by the DCC, and they include monthly and quarterly reports to the FRIEND Collaborative group on accrual, data quality and study compliance and reports presented in the packet produced for each Steering Committee and DSMB. Statistical reports include reports to the FRIEND Collaborative group from the data analysis, and special reports for scientific manuscripts.

Statistical Reports will be generated in SAS. Reports are provided for DSMB reviews, and for final analysis of study results in preparation for scientific publications. The content of the interim reports will be very complete and will serve as the template for the final report of each study, which in turn will form the basis of the publication of the results. Our proposed reports to the DSMB would include the following: a protocol description and history; accrual rates; site

performance in terms of accrual; eligibility; protocol violations; data accuracy and minority representation; patient characteristics by treatment and site; and the rate of adverse experiences.

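### Section 4.3.6 takes women at 3 x ULN out of the study rather than only off drug, and no by-arm peak or count of liver elevations is planned: a cheap improvement that affects few women

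*Combined protocol and SAP*

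**What the plan says.** Section 4.3.6 sets out two dispositions in one paragraph.

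- **Related SAE.** It ends the assigned intervention, and the "participant will be followed up for cycle outcome and will contribute research data towards intent-to-treat analyses". Allergic reactions and liver toxicity are named as included.
- **Liver test at 3 x ULN.** The woman "will be terminated from the study and will return to site for repeat testing every 48 hours until resolution". An isolated value of this kind need not be an SAE.

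The same section sends all liver toxicity reports to the DSMB. It stops the trial if three or more participants develop active liver disease, defined as ALT or AST at 8 x ULN or more, or at about 3 x ULN with raised bilirubin or INR, or with symptoms.

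Section 2.6 lists "Changes in liver function between the 3 groups" as a secondary outcome. Section 2.7 says that "the changes in liver function, estrogen levels, endometrial thickness, and follicular measurements will be presented for the three treatment groups", using n, mean, SD, median and interquartile range, with differences taken from screening to Visits 1, 2 or 4. It adds that "a two-way ANOVA will be used to compare the effects of the three treatments and the presence of fibroids on the above outcome parameters". Section 6.4 repeats this: "the changes in liver function, hormone levels, endometrial thickness and follicular measurements will be presented for the three treatment groups". Both sections call the analysis descriptive and underpowered for formal inference.

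On safety reporting, Section 7.3.4 has the DCC provide "study-wide summary statistics (not filtered by treatment group) of adverse events to the single IRB annually". Section 7.8 lists for the DSMB "patient characteristics by treatment and site; and the rate of adverse experiences". The DSMB Charter (Appendix K, report schedule) adds safety data, AEs, SAEs, and drop-outs with reason and time point.

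**The concern.** Section 4.3.6 itself separates ending treatment from ending participation, so a site could reasonably take the second rule at its word. The woman who leaves the schedule would then leave because of the outcome being studied. The by-arm liver summary at Visit 4 would describe only women who had not been flagged before.

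The second gap exists even with complete data. Section 5.2 says that the results will be used to confirm hepatic safety for the larger FRIEND study, and Section 2.4 says that the combination arms were added because toxicity might change when the drugs are given together. The arm in which a liver elevation arose, and how high it went, is therefore what the next study needs to know. No planned output states it.

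**Working it through.** The plan gives no figure on this point to reproduce. The check sets the text against the visit schedule, then sizes the effect.

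**1. What a literal reading removes.** Sections 2.4 and 4.3.3 place liver panels and estrogen at screening and Visits 1, 2 and 4, the follow-up ultrasound at Visit 3, and the final folate at Visit 4.

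| Flagged on bloods from | Value enters that visit's by-arm summary | Scheduled visits lost |
|---|---|---|
| Visit 1 | Yes | 2, 3 and 4 |
| Visit 2 | Yes | 3 and 4 |
| Visit 4 | Yes | None |

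The Visit 1 row assumes that the result arrives after she is randomised that day. The repeat tests continue after a flag, but no section says whether they enter the by-arm analysis. Stopping drug ends on-treatment EGCG profiles under either rule, so the wording itself costs no on-treatment pharmacokinetic data.

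**2. Effect on the Visit 4 mean.** Equal randomisation of 36 gives 12 per arm. Assume 11 women at 0.5 x ULN and one still at 5 x ULN. The mean with her is (11 x 0.5 + 5)/12 = 0.875 x ULN; without her it is 0.50 x ULN. If she has returned to 0.5 x ULN by Visit 4, the difference is zero.

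**3. How many women.** No document gives a 3 x ULN rate. Section 4.4.2 gives under 5% for transient transaminase elevations and places toxicity mainly at 3-4 months. Dosing lasts up to 2 months (Section 4.3.2). Taking 1% to 5% as an assumed range:

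- Flagged at any time: 36 x 0.01 = 0.36 to 36 x 0.05 = 1.8 women.
- Flagged before Visit 4, if each of the three on-EGCG draws is equally likely (assumed): 0.36 x 2/3 = 0.24 to 1.8 x 2/3 = 1.2 women.
- Chance of at least one: 1 - (1 - 0.01 x 2/3)^36 = 0.21 to 1 - (1 - 0.05 x 2/3)^36 = 0.70.

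The upper ends are generous. The 5% covers elevations of any size, and late onset would move flags towards Visit 4, where nothing is lost. If every flag came at Visit 4, the number losing data would be 0.

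**4. What the planned statistics show.** Take one arm of 12, six per fibroid stratum, with one woman rising from 20 to 120 U/L (assumed ULN 40) and every other change in the trial set to zero.

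- Mean = 100/12 = 8.3; SD = sqrt[(11 x 8.33² + 91.67²)/11] = 28.9; median 0; IQR 0 to 0. The other arms show 0 and 0.
- Two-way ANOVA with interaction, rise x: treatment mean square = 12 x [(x/18)² + 2(x/36)²]/2 = x²/36; error mean square = (5/6)x²/30 = x²/36; F(2,30) = 1.0, p = 0.38.
- Two cases in the arm: F = 2.0 to 2.5, p = 0.15 to 0.10. Three cases: F = 3.46 to 5.0, p = 0.04 to 0.01.

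So the mean and SD hint at a large outlier, while the median and IQR do not. None of them says how many women reached 3 x ULN or how high they went.

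**5. Other outputs.** The annual IRB summary is pooled across arms. Section 7.8 and the DSMB Charter do not state that AEs or drop-outs are shown by arm. The stopping rule counts cases trial-wide, and a symptom-free, isolated rise between 3 and 8 x ULN does not count towards it.

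**The case against.** The strongest reply is that little liver information is lost. A flagged woman's abnormal value is already in the summary for the visit at which it was found. She is then tested more densely than the schedule requires, and Section 7.3.3 follows events to resolution or stabilization. The planned n would show an arm falling from 12 to 11, and the Charter's drop-out report would give her reason and timing. The trial is open-label and the DCC Data Manager is unblinded, so a by-arm count could be produced at any time. The sponsor may also have meant termination of treatment, which fits the sentences just before. All of this stands, and it limits the point to a wording repair and a missing table.

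Three stronger readings are tempting, and the documents support none of them.

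- **That liver cases escape safety oversight.** They do not: AE recording, DSMB review of every liver toxicity report and the three-case stopping rule all remain.
- **That the two rules contradict each other for every woman at 3 x ULN.** They compete only for a woman who also has a related SAE.
- **That the ANOVA would hide hepatotoxicity.** The study declares itself descriptive, so its p-value carries little weight, and F = 1.0 for any size of rise results from setting all other changes to zero. A count is no sharper as a test: one-sided Fisher, 12 against 24, gives 12/36 = 0.33, 66/630 = 0.10 and 220/7140 = 0.03 for one, two and three cases. The table is worth having as description.

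What the reply does not meet is that no section plans a by-arm peak or count, or settles the status of the repeat values.

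**Conclusion.** The point holds as a low-cost improvement. Followed to the letter, Section 4.3.6 drops women from later scheduled visits because of a safety outcome, and Sections 2.7 and 6.4 leave out the by-arm liver description that a study meant to confirm hepatic safety should prespecify.

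The size is small. Probably none or one of the 36 women would lose later data. That judgement rests on an assumed 3 x ULN risk, with the stated onset of 3-4 months pointing to the low end of the range. The Visit 4 distortion is close to zero if values have resolved by then. The missing table does not depend on these assumptions, since it would be missing with complete data too. Neither the primary pharmacokinetic comparison nor participant safety is put in doubt.

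**What to change.** - **Section 4.3.6.** Replace termination from the study with: the woman stops study drug and remains in scheduled safety follow-up (liver, estrogen, folate, ultrasound), with no 8-hour EGCG profile after stopping. Keep the 48-hour repeat-testing clause as it is.
- **Sections 2.7 and 6.4.** Keep all randomised women in the safety summaries and include unscheduled liver values. Report descriptively, by arm, the peak ALT, AST and bilirubin and the number of women at or above 3 x ULN. Show elevations on Visit 1 bloods separately: EGCG starts at screening and clomiphene or letrozole is dispensed only at Visit 1, so these arise on EGCG alone.

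The cost is one sentence, one analysis rule, one extra table, and up to three retained visits (Visits 2, 3 and 4) per flagged woman. No new assays are needed.

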### 4.4 Risk/Benefit Assessment

#### 4.4.1 Possible Benefits

No direct benefits to participants.

#### 4.4.2 Possible risks/discomforts

Blood draws: Discomfort, bruising, infection or bleeding at the needle puncture site

Pelvic ultrasound: abdominal or pelvic discomfort

EGCG: Gastrointestinal upset; rare liver toxicity. The literature supports a potential relationship between high-dose Green Tea extract consumption and transient changes in serum liver enzymes. Rare ( $<5\%$ ) and transient liver transaminase elevations have been documented. Hepatotoxicity tended to show a temporal relationship between Green Tea extract consumption and effect onset with Green Tea extract-induced toxicity mainly manifesting after roughly 3-4 months of consumption. Daily intake of 1315 mg of Green Tea catechins containing 843 mg EGCG poses mainly mild, transient hepatic adverse effects. The incidence and severity of hepatotoxicity increased when Green Tea extract or EGCG was administered under fasted conditions, while exposure to Green Tea under fed conditions appears to alleviate such risk.

Clomiphene Citrate: Visual changes (such as blurring of vision, double vision, floaters), abdominal pain, nausea, vomiting, constipation, mood changes, headache, hot flashes, fatigue, abnormal endometrial thickening, multiple pregnancies, formation of ovarian cyst, breast discomfort, abnormal uterine bleeding, and bloating

Letrozole: Fatigue, dizziness, nausea, hot flashes, arthritis pain in your joints, back pain, increased cholesterol levels, formation of ovarian cysts, multiple pregnancies

Other risks: There is also the risk of loss of confidentiality. Filling out the questionnaires may make the subjects uncomfortable or feel some anxiety. There is a risk that information about the subject may become known to people outside of this study.

As this is a NIH (NICHD) funded study, your study information is protected by a Certificate of Confidentiality. This Certificate allows us, in some cases, to refuse to give out your information even if requested using legal means.

It does not protect information that we have to report by law, such as child abuse or some infectious diseases. The Certificate does not prevent us from disclosing your information if we learn of possible harm to yourself or others, or if you need medical help.

Disclosures that you consent to in this document are not protected. This includes putting research data in the medical record or sharing research data for this study or future research. Disclosures that you make yourself are also not protected.

## 5 Study Design

### 5.1 Type of Design

This will be a randomized, open-label, multi-center, pharmacokinetics and hepatic safety trial of EGCG with 36 total patients in 3 treatment arms. The randomization scheme will be coordinated through the DCC and the randomization will be stratified for age groups 18-29 and 30-40 and presence of uterine fibroids.

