#### 4.3.3 Study Summary

Recruitment and Prescreening: see Section 5 descriptions following.

Screening visit (anytime in cycle 1):

1. Obtain informed, signed consent.
2. Complete medical/gynecological/menstrual history and physical exam of female study participant.
  - Vital signs, height, weight, hip and abdominal circumference, BMI
  - Pap smear if necessary per current ACOG time-frame guidelines
  - Standard pelvic and breast exam conducted by physician or within past 12 months
3. Perform radiological exams.
  - Pelvic ultrasound measuring uterine and ovarian characteristics or within past 3 months
4. Laboratory tests: EGCG and metabolites, liver function, folate, estrogen levels, genetics sample collection and urine pregnancy test.
5. Dispense Green Tea extract and educate on dietary restrictions while taking Green Tea extract and with the importance of taking food. All patients to start Green Tea extract at this visit.
6. Contraception education. Patients will be counseled to use non-hormonal double-barrier method: a male/female condom plus spermicidal agents, cervical cap, diaphragm or sponge.
7. Concomitant medication collection.

Visit 1 (Day 1-5):

Patient will be seen on menstrual cycle day  $3 \pm 2$  days for clomiphene citrate/letrozole initiation visit

1. Vital signs and weight.
2. Laboratory tests: EGCG levels over 8 hours (0.5,1,2,4,6,8), liver function, folate, estrogen level, and urine pregnancy testing.
3. Concomitant medication collection and pill counts of EGCG.
4. Randomization and dispensation of clomiphene citrate/letrozole.
5. Contraception education. Patients will be counseled to use non-hormonal double-barrier method: a male/female condom plus spermicidal agents, cervical cap, diaphragm or sponge.

Visit 2 (day 8-10):

Patient will return several days after final clomiphene citrate/letrozole administration

1. Vital signs and weight.
2. Laboratory tests: EGCG levels over 8 hours (0.5,1,2,4,6,8), liver function, folate, estrogen level and urine pregnancy testing.

3. Concomitant medication collection and pill counts of EGCG and clomiphene citrate or letrozole as appropriate.
4. Contraception education. Patients will be counseled to use non-hormonal double-barrier method: a male/female condom plus spermicidal agents, cervical cap, diaphragm or sponge.

Visit 3 (day 14-16):

1. Pelvic ultrasound via a transvaginal probe or transabdominal transducer evaluation of endometrial thickness and ovarian characteristics.

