## 5.7 Transvaginal Ultrasound Exam

An ultrasound exam will be performed with a transvaginal probe. For subjects who cannot tolerate a transvaginal probe, a transabdominal ultrasound evaluation will be performed. The following measures will be obtained at screening: uterine dimensions, leiomyoma presence and size, other uterine abnormalities, endometrial thickness, ovarian size in three dimensions, the size of the largest ovarian follicle, follicle count in the largest plane and ovarian morphology. Ovarian size is determined by measuring the largest plane of the ovary in two dimensions and then turning the vaginal probe 90 degrees and obtaining a third measurement. Endometrial thickness is the largest anterior-posterior measurement of the endometrium in the sagittal plane. Ovarian volume is determined by the formula for a prolate ellipsoid (length x width x height x  $\pi/6$ )(Pache, Hop et al. 1991). If the patient has had no prior test of tubal patency, this may be the desired time to perform a sonohysterogram to determine tubal patency. Only endometrial thickness and ovarian follicular measurements will be measured at visit 2.

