### 6.3 Secondary Outcome Measurements

The secondary outcome parameters will include:

- Changes in liver function between the 3 groups.
- Changes in estrogen levels (E2) between the 3 groups.
- Changes in endometrial thickness and ovarian characteristics between the 3 groups.
- Change in the pharmacokinetic parameters of EGCG and metabolites within each group.

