### *7.5.3 Data Quality Control*

The site PI will be responsible for ensuring that study related tests are performed by competent personnel. The criteria for determination of competency may vary between sites in the study. Attempts will be made to standardize protocols whenever possible to minimize inter-site variation.

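### No step in the plan keeps the person scanning unaware of the arm, so expectation could bias the between-arm ultrasound comparison, a secondary outcome

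*Combined protocol and SAP*

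**What the plan says.** - **Design.** Section 5.1: "This will be a randomized, open-label, multi-center, pharmacokinetics and hepatic safety trial of EGCG with 36 total patients in 3 treatment arms".
- **Outcome.** Section 6.3 (and 2.6) lists as secondary: "Changes in endometrial thickness and ovarian characteristics between the 3 groups".
- **Analysis.** Section 2.7 states that "endometrial thickness, and follicular measurements will be presented for the three treatment groups", and then names a two-way ANOVA of treatment and fibroid status on these parameters at alpha 0.05. The section under heading 6.4 repeats this. Both describe the analysis as mainly descriptive and the study as underpowered for formal inference.
- **Timing.** Section 4.3.3 places this step at Visit 1: "Randomization and dispensation of clomiphene citrate/letrozole". Visit 3 consists of one item: "Pelvic ultrasound via a transvaginal probe or transabdominal transducer evaluation of endometrial thickness and ovarian characteristics".
- **Measurement rule.** Section 5.7: "Endometrial thickness is the largest anterior-posterior measurement of the endometrium in the sagittal plane". It also asks for the size of the largest follicle and a follicle count in the largest plane.
- **Standardization.** Section 7.5.3: "The criteria for determination of competency may vary between sites in the study", followed by "Attempts will be made to standardize protocols whenever possible to minimize inter-site variation".
- **Blinding.** The only statements about blinding in this trial's conduct are in the DSMB charter. One concerns a pooled pregnancy rate and the other says the data manager at the coordinating center is not blinded. Neither concerns ultrasound.

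**The concern.** Open-label treatment does not require an open-label reader. EGCG levels, liver tests and estradiol come from a laboratory. An endometrial thickness or a follicle count depends on which plane the operator freezes and where the calipers are placed. If the operator knows the arm and expects a particular finding, that choice can shift the reading in one direction within an arm.

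The plan supplies reasons for such expectations. Section 2.4 presents clomiphene and letrozole as drugs for ovulation stimulation. Section 4.4.2 lists abnormal endometrial thickening for clomiphene only, ovarian cysts for both add-on drugs, and neither for EGCG.

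At stake is the ultrasound comparison between arms. Calling it descriptive does not protect it: a biased arm mean is still biased when it is only tabulated, and an ANOVA is specified as well.

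**Working it through.** **1. Can the arm be known when the outcome is measured?** Allocation and dispensing are at Visit 1 and the add-on tablet count is at Visit 2. Section 4.3.3 puts the follow-up scan at Visit 3, while section 5.7 puts the follow-up measurements at visit 2. Both fall after allocation, so the point does not depend on that discrepancy. The screening scan precedes randomization, so only the follow-up reading is exposed.

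**2. Is there a safeguard?** The supplied text mentions no masked operator, masked central reading, stored images or duplicate reading. The commitment in section 7.5.3 concerns variation between sites, not knowledge of the arm.

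**3. The plan's own figures.** Sections 2.7 and 6.4 state power of 0.44 and 0.85 for effect sizes f = 0.25 and 0.40 with N = 36. With a noncentral F, λ = f²N, and 2 and 30 degrees of freedom (36 women minus 6 cells), the treatment test has power 0.23 and 0.52, so the stated pair does not reproduce. That is a separate matter. Only the label medium for f = 0.25 is used here.

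**4. The medium effect in SD units.** If one of three equal arms differs from the other two by d SD, f = d·√2/3. Hence d = 0.25 × 3/√2 = 0.53. The same formula applies if two arms shift together against the third.

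**5. Size of an assumed reading bias.** The documents give no SD and no bias. Assumed: bias 0.5 to 1.0 mm, SD 1.5 to 2.5 mm. The ratio bias/SD is:

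| Bias | SD 1.5 mm | SD 2.0 mm | SD 2.5 mm |
|---|---|---|---|
| 0.5 mm | 0.33 | 0.25 | 0.20 |
| 0.75 mm | 0.50 | 0.38 | 0.30 |
| 1.0 mm | 0.67 | 0.50 | 0.40 |

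Only one of the nine cells exceeds 0.53.

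**6. What such a bias would do to the ANOVA.** With 12 women per arm, no true difference, and one arm (or both add-on arms) read d SD too high, λ = 36 × 2d²/9 = 8d². The chance that the treatment test rejects at 0.05 is:

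| d | λ = 8d² | P(reject) |
|---|---|---|
| 0 | 0 | 0.05 |
| 0.20 | 0.32 | 0.07 |
| 0.30 | 0.72 | 0.10 |
| 0.375 (midpoint) | 1.125 | 0.13 |
| 0.50 | 2.00 | 0.21 |
| 0.67 | 3.56 | 0.34 |

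**7. Sensitivity to the SD.** The outcome is a change. The screening scan may fall at any point of the cycle or come from the previous 3 months, so the SD of change could exceed the range assumed above. If it were 3 to 4 mm (also an assumption), the same bias would be 0.5/4 = 0.125 to 1.0/3 = 0.33 SD, below 0.53 throughout.

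**The case against.** The strongest case on the other side has five parts.

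- **Nothing shows that the sonographer knows the arm.** Visit 3 lists only the scan, with no dispensing, tablet count or medication review. This stands. A reader might infer from the open-label design that the operator is always aware of the allocation. The documents show only that nothing prevents it.
- **The expectation is uneven.** A reader might infer that the risk section names endometrial effects for both added drugs. It names thickening for clomiphene only. Cysts are listed for both, which could set the add-on arms apart from EGCG alone but not from each other, and a cyst is not the measurement analyzed. This stands and narrows the argument. The ovulation-stimulation purpose of both drugs remains a source of expectation about follicles.
- **Operator discretion is limited.** Section 5.7 fixes the endometrial rule and the follicle-count plane. This stands in part, because finding the largest plane or diameter is still the operator's judgement.
- **Masking may be described elsewhere.** Section 7.6 mentions Manuals of Procedures, which were not supplied. This cannot be excluded. If they cover it, one sentence in 5.7 settles the point.
- **Little depends on these outcomes.** The aims are pharmacokinetics and hepatic safety, section 4.2 gives no secondary aim, and the plan calls its analysis descriptive and underpowered. This stands as to importance. It does not remove a bias from a comparison the plan intends to report.

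**Conclusion.** The point holds as a minor one. A between-arm secondary outcome is measured after allocation with operator judgement, and no supplied text keeps the operator unaware of the arm. Expectation could bias it; the documents do not show that it will.

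The size rests wholly on assumed values. It is 0.20 to 0.67 SD for a bias of 0.5 to 1 mm and an SD of 1.5 to 2.5 mm, and smaller if the SD of change is larger. A reader might infer that even a small reading bias equals the plan's medium effect. That is not supported: 0.53 SD is passed only when the largest assumed bias meets the smallest assumed SD.

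Nor should a reader infer that the trial's main conclusions are at risk, since the primary pharmacokinetic results and the liver tests are laboratory values.

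**What to change.** In section 5.7, add that, where feasible with existing staff:

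- the person who performs and measures the post-randomization scan is not told the arm;
- the scan request carries only the study ID;
- women are asked not to mention their tablets to the operator;
- measurements are recorded before any treatment pages are opened.

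Add one CRF box recording whether the operator knew the arm. Where masking is not possible, the site flags the scan and need not find another operator, so that readers can see how many readings were exposed.

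While 5.7 is open, its visit for the follow-up measurements and the visit given in 4.3.3 must be reconciled.

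**Cost.** A short instruction and one data field, with the same visit and the same scan. Small sites where the prescriber also scans will have some scheduling effort. Masking may be imperfect, because visible follicles can themselves suggest the arm; the CRF box helps to show where it failed.
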